# **RESEARCH QUESTIONS**

- What is the difference in the tube-related complication rates after placing a purse-string suture (U suture placement and retention) for thoracostomy wound re-approximation versus non-placement of purse-string at the time of chest tube insertion?
- What is the difference in the early and late complication rates after using a purse-string suture (U suture) for thoracostomy wound re-approximation versus use of only an occlusive adhesiveabsorbent dressing with unreapproximated thoracostomy wound edges; at the time of chest tube removal?
- What is the difference in pain score after using a purse-string suture (U suture) for thoracostomy wound re-approximation versus use of only an occlusive adhesive-absorbent dressing with unreapproximated thoracostomy wound edges; after chest tube removal?
- Is purse-string thoracostomy wound closure associated with more cosmetic complications of thoracostomy scar in the long term than un-reapproximated thoracostomy edges with an occlusive adhesive-absorbent dressing ?

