# STUDY VARIABLES AND DEFINITION

The independent variables to be employed for the analysis include:

- Age of the patient
- Sex of the patient
- Presence of specific co-morbidities (Diabetes, Hypertension, Chronic Liver disease, Chronic kidney disease)
- Charleson Comorbidity Index
- History of cigarette smoking and estimated pack years if positive

- Use of steroids and chemotherapeutic agent
- Abnormal Body mass index (Obesity(BMI> 30kg/m^2), Malnutrition(BMI< 18kg/m^2)

The Dependent variables to be employed for the analysis include:

- Presence of severe pain at the chest tube site after chest tube insertion (Average daily pain score after tube insertion > 5 on the Visual Analog Scale and or Numerical Rating Scale)
- Occurrence of tube dislodgement after chest tube insertion
- Occurrence of peri-tubal leakage of fluid after chest tube insertion
- Presence of wound air suck-in after chest tube removal (indicated by presence of air suck-in sound through the wound into the pleural space during quiet and or forced inspiration)
- Occurrence of wound infection after chest tube removal (presence of purulent or offensive wound discharge with or without fever or presence of wound discharge that is microbiologically positive)
- Occurrence of wound dehiscence after chest tube removal
- Occurrence of early (within 7 days) and late pneumothorax (more than 1 week) after chest tube removal confirmed on chest radiography
- Development of raised or elevated thoracostomy wound scars (unsightly scars appearing like hypertrophic scars or keloids) within 3 months of chest tube removal

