assistance. To ensure synchrony, a short count of one to three is done by the lead surgeon and by the count of three, he completes the knotting down to close the wound just as the tube is rapidly pulled out at a single swipe by the assistance upon completion of the count of three. There will be regular rehearsals and practice of these synchronous actions by all those who will be involved with this study as surgeons and assistants. The wound must be closed to air and water tightness but without strangulating the edges. The suture is trimmed, and a sterile dressing applied as before. There will be strict observance of aseptic technique by all involved in this tube removal process. A chest radiograph is done immediately after to check for presence of iatrogenic pneumothorax. The wound dressing will be removed on the third day and subsequent wound care will be determined by the finding at wound review by the principal investigator on this third day. The protocol to follow will be to continue daily povidone iodine wound care if there is evidence of wound infection but to leave the wound open to fresh air and apply povidone iodine topical cream till the suture is removed by day 7, after tube removal. The pain score will be assessed on a continuous basis (everyday till patient is discharged home and at every contact in the outpatient clinic). The patients will be followed up once a month for atleast 3 consecutive months after chest tube removal. Their pain score, wound outcomes and serial chest radiographic check (immediately after tube removal, at one week after tube removal and at every follow up visit in the outpatient clinic), will be done.

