#### 5) Follow up and treatment adherence

The patients in both groups will be followed up once every month for atleast three consecutive months assessing for evidence of wound infection, pain control and with chest radiography for evidence of pneumothorax. The wound will also be assessed for development of raised or elevated thoracostomy wound scars (unsightly scars appearing like hypertrophic scars or keloids) within 3 months of chest tube removal.

Patients with wound infection will have 10% povidone iodine daily dressing with institution of antibiotic therapy as per unit protocol. All patients with poor pain control (Pain score greater than 5),

involved with in this study, will have their pain control drug regimen escalated as per unit protocol to achieve better pain control.

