#### DATA ANALYSIS AND MANAGEMENT

The data will be entered into the computer and thorough data cleaning will be done to check for errors and omissions at the end of data collection. The data was analyzed using Statistical Package for Social Sciences (SPSS) version 21. Descriptive statistics for baseline data shall be analyzed using mean, standard deviation, range and median, where appropriate, for any continuous variable and as percentages for any categorical variable. Baseline characteristics of the two study arms will be compared using Chi-square tests (for categorical variables) and student's t-test or analysis of variance (for continuous variables). Risk of complication will be evaluated using Cox-proportional analysis adjusting for potential confounders. Level of significance will be set at 5%. Findings will be presented in forms of texts, tables, figures and graphs as appropriate.

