(33) USE OF THERAPEUTIC A	ANTIBIOTICS YES() NO()	
IF YES, INDICATE THE GENE	ERIC TYPE , DOSE, FREQUENCY	AND DURATION IN DAYS
	R CHEST TUBE INSERTION):	,
PNEUMOTHORAX:	YES()	NO ( )
TUBE DISLOGDEMEN		NO ( )

SERIAL NO: .....

EMPYEMA:	YES ( )	NO ( )
WOUND INFECTION:	YES ( )	NO ( )
WOUND DEHISCENCE:	YES ( )	NO ( )
FLUID LEAKAGE:	YES ( )	NO ( )
AIR LEAK:	YES ( )	NO ( )
PAIN:	YES ( )	NO ( )

PAIN SCORE: DAY 1	6AM ( )	6PM( )
DAY 2	6AM ( )	6PM( )
DAY 3	6AM ( )	6PM( )
DAY 4	6AM ( )	6PM( )
DAY 5	6AM ( )	6PM( )
DAY 6	6AM ( )	6PM( )
DAY 7	6AM ( )	6PM( )
DAY 8	6AM ( )	6PM( )
DAY 9	6AM ( )	6PM( )
DAY 10	6AM ( )	6PM( )

# SERIAL NO: .....

(35) COMPLICATIONS (IMMEDIATELY AFTER CHEST TUBE REMOVAL):

PNEUMOTHORAX ON IMMEDIATE POST-TUBE REMOVAL CHEST XRAY: YES ( ) NO ( )

PNEUMOTHORAX ON CHEST XRAY DONE AFTER 1 WEEK:

	YES ( )	NO ( )
EMPYEMA:	YES ( )	NO ( )
WOUND INFECTION:	YES ( )	NO ( )
WOUND DEHISCENCE:	YES ( )	NO ( )
FLUID LEAKAGE:	YES ( )	NO ( )
AIR SUCK-IN THROUGH WOUN	ID:	
	YES ( )	NO ( )
MAJOR PAIN:	YES ( )	NO ( )
PAIN SCORE:		
DAY 1	6AM ( )	6PM()
DAY 2	6AM ( )	6PM()
DAY 3	6AM ( )	6PM()
DAY 4	6AM ( )	6PM()
DAY 5	6AM ( )	6PM()
DAY 6	6AM ( )	6PM()
DAY 7	6AM ( )	6PM()
DAY 8	6AM ( )	6PM()
DAY 9	6AM ( )	6PM()
DAY 10	6AM ( )	6PM( )

### (36) COMPLICATIONS AT FOLLOW-UP 1

PNEUMOTHORAX ON FOLLOW UP CHEST XRAY:

	YES ( )	NO ( )
WOUND INFECTION:	YES ( )	NO ( )
WOUND DEHISCENCE:	YES ( )	NO ( )

SERIAL NO:		
HYPERTROPHIC SCAR:	YES ( )	NO ( )
KELLOID:	YES ( )	NO ( )
WOUND PAIN:	YES ( )	NO ( )
IF YES, PAIN SCORE:		

# COMPLICATIONS AT FOLLOW-UP 2

WOUND INFECTION:	YES ( )	NO ( )
WOUND DEHISCENCE:	YES ( )	NO ( )
HYPERTROPHIC SCAR:	YES ( )	NO ( )
KELLOID:	YES ( )	NO ( )
WOUND PAIN:	YES ( )	NO ( )
IF YES, PAIN SCORE:		
PAIN SCORE:	6AM ( )	6PM ( )

# COMPLICATIONS AT FOLLOW-UP 3

WOUND INFECTION:	YES ( )	NO ( )
WOUND DEHISCENCE:	YES ( )	NO ( )
HYPERTROPHIC SCAR:	YES ( )	NO ( )
KELLOID:	YES ( )	NO ( )
WOUND PAIN:	YES ( )	NO ( )
IF YES, PAIN SCORE:		
PAIN SCORE:	6AM ( )	6PM ( )

# COMPLICATIONS AT FOLLOW-UP 4

WOUND INFECTION:	YES ( )	NO ( )
WOUND DEHISCENCE:	YES ( )	NO ( )
HYPERTROPHIC SCAR:	YES ( )	NO ( )
KELLOID:	YES ( )	NO ( )

SERIAL NO:		
WOUND PAIN:	YES ( )	NO ( )
IF YES, PAIN SCORE:	·	
PAIN SCORE:	6AM ( )	6PM ( )
COMPLICATIONS AT FOLLO	W-UP 5	
WOUND INFECTION:	YES ( )	NO ( )
WOUND DEHISCENCE	E: YES()	NO ( )
HYPERTROPHIC SCAF	R: YES ( )	NO ( )
KELLOID:	YES ( )	NO ( )
WOUND PAIN:	YES ( )	NO ( )
IF YES, PAIN SCORE	:	
PAIN SCORE:	6AM ( )	6PM ( )

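### Does the research question on pain score after tube removal need an outcome line and an analysis that the plan does not give?

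*Combined protocol and SAP*

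**What the plan says.** Research Questions, third item: "What is the difference in pain score after using a purse-string suture (U suture) for thoracostomy wound re-approximation", set against an occlusive dressing alone, with the period being after tube removal.

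Study Variables and Definition lists the dependent variables. The only pain item is severe pain at the tube site, defined as "Average daily pain score after tube insertion > 5 on the Visual Analog Scale and or Numerical Rating Scale". The items tied to tube removal are air suck-in, infection, dehiscence, pneumothorax and scarring.

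Data Analysis and Management has one sentence on outcomes: "Risk of complication will be evaluated using Cox-proportional analysis adjusting for potential confounders". The tests for categorical and continuous variables belong to a different sentence, which begins "Baseline characteristics of the two study arms will be compared using Chi-square tests".

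On data collection, the Group A text of Procedure for chest tube removal has pain scored "everyday till patient is discharged home and at every contact in the outpatient clinic". Follow up and treatment adherence covers both groups at monthly visits, "assessing for evidence of wound infection, pain control and with chest radiography". The Study Proforma has a morning and an evening score for each of 10 days after removal, a yes/no box for major pain, and pain fields at each follow-up visit, including one headed "IF YES, PAIN SCORE".

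**The concern.** The plan asks for a difference in scores and then appears not to provide for one. The listed pain variable is binary and belongs to the wrong period. A Cox model returns a hazard ratio for an event, not a difference in scores. The t-test is reserved for baseline data.

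The form adds three doubts.

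- Score cells carry no scale label, although Management of indwelling chest tubes uses three scales.
- Follow-up 1 takes a score only from patients who report wound pain. Later visits have both a conditional field and separate morning and evening cells.
- The sentence on daily scoring sits in the Group A text and is not repeated for Group B.

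In an open-label trial with a patient-reported outcome, a scale, day and method chosen after the data are seen could shape the pain result. If only patients in pain were scored, the comparison would rest on a subgroup formed after randomisation.

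**Working it through.** The plan gives no figure for pain, neither an SD nor a target difference, so there is none to reproduce. The check sets the sections side by side, with one piece of algebra.

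**1. Is the outcome excluded?** It is not in the list of dependent variables. That list is introduced as what the variables include, so it does not rule out a score that a research question names and the form collects.

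**2. Are the data there, in both arms?** The form gives 10 days × 2 = 20 score cells after removal, none conditional on a yes/no answer. Clinic scoring in the Group A text is also unconditional. For Group B, the removal text omits the sentence, but the follow-up section assesses pain control in both groups and the form is the same for all patients.

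**3. Does the conditional field bias the comparison?** Let a share pA of Group A and pB of Group B report wound pain at a visit, with the same mean score m among those in pain.

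- Scores of patients in pain only: m − m = 0.
- All patients, with no pain scored 0: [pA × m + (1 − pA) × 0] − [pB × m + (1 − pB) × 0] = m × (pA − pB).

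The first line misses a real difference whenever pA and pB differ. It applies only if the analyst discards patients recorded as having no pain. The form records wound pain yes or no for every patient at every visit, so the second line can be computed. Follow-ups 2 to 5 also have morning and evening cells that do not depend on the answer. Only follow-up 1 relies wholly on coding no as 0.

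**4. Is the scale open?** Of the three scales, the outcome definition uses the visual analogue and numerical rating scales, and the protocol calls both superior to the verbal scale. The choice is between two numeric scales.

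**5. Is there a natural time point?** Both removal texts provide for a decision on the wound by the principal investigator at, or after at least, three days. Both also schedule a radiograph at one week. In Group A the suture stays "till the suture is removed by day 7, after tube removal", so a one-week score may fall before or after its removal. Suture removal is part of the assigned closure method, so either reading still compares the methods as assigned. The day-3 and monthly assessments avoid the question.

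**6. Is any post-removal pain analysis implied?** The form files major pain under complications after removal, and complications are what the Cox model evaluates. The box itself is undefined. The follow-up section treats a score above 5 as poor control, the same cut-off as in the outcome definition. A binary comparison can therefore be read into the plan. It would not give the score difference that the question asks for.

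**The case for a change.** The strongest case for a change is that the two central observations are correct: no post-removal pain score is listed as an outcome, and no sentence compares scores between arms. Suture-related pain is part of the protocol's own case for the trial in Problem Statement. With 20 in-hospital cells and several visits per patient, two usable scales and no stated summary, many analyses are possible. The treatment is open to patient and surgeon. Naming a scale and a main time point would cost only a few lines, and a score that was never labelled or taken may not be recoverable later.

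The omission and the freedom it leaves both stand. A pain result from this trial will be read as supporting evidence, and a report should say how the scale and day were chosen.

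The claim that the form blocks a sound score analysis does not stand, because a coding rule settles the conditional field. Nor does the claim that pain after removal has no estimate of any kind, since a binary comparison is arguably covered. Detectable-difference calculations do not help either way: they need a pain SD that the documents do not give, and they describe a possible analysis without measuring the omission.

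**Conclusion.** No change to the plan is needed. This is a gap in written detail that analysts fill sensibly: take the post-removal scores on one numeric scale, compare the assigned arms, and report a mean difference with its 95% confidence interval. No stated rule in the plan leads to a wrong result.

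The extent is one of four research questions. Post-removal pain score is absent from the three specific objectives, and the sample size rests on acute pneumothorax.

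The conclusion rests on three assumptions: the common form is completed in both arms, the scale behind each recorded score can be identified, and patients who report no wound pain at a visit are scored 0 and kept in the comparison. If those patients were left out, the bias shown in step 3 would be real at follow-up 1 and wherever only the conditional field is used.

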#### CHAPTER TWO

#### LITERATURE REVIEW

#### MANAGEMENT OF THORACOSTOMY WOUND AFTER CHEST TUBE REMOVAL

The common indications for chest tube drainage are listed in Table 1 below. Chest tube insertion is not devoid of risks (17). Closed tube thoracostomy wounds are often classified as "clean contaminated" and hence the risk of wound infection is 7.7% (18). The goal of prophylactic antibiotic therapy for closed tube thoracostomy drainage in traumatic chest injury is to decrease the risk of infectious complications and its associated morbidities, based on reasonable assumptions about the organisms most often cultured (19). Antibiotic prophylaxis should be considered for trauma patients requiring pleural drains, especially after penetrating trauma and a single dose of cephazolin 2g, given intravenously has been suggested, to provide adequate antimicrobial cover (10). A meta-analysis showed that prophylactic antibiotic treatment reduces the risk of developing infectious complications after tube thoracostomy for traumatic injuries of the chest, with the effect best documented for penetrating injuries (16). However, a single-dose antibiotic prophylaxis in penetrating chest trauma is as effective as prolonged prophylaxis (20). Early physiotherapy and early removal of the thoracostomy tube are important to prevent intrathoracic sepsis (20). Antibiotic prophylaxis is not recommended for non-trauma patients requiring a pleural drain (10).

Table 1. The common indications for chest tube insertion (9).
1) Pneumothorax
Large or symptomatic primary spontaneous pneumothorax
Secondary spontaneous pneumothorax
Pneumothorax in patients on mechanical ventilation
Tension pneumothorax
Large or symptomatic iatrogenic/traumatic pneumothorax
Occult traumatic pneumothorax associated with hemothorax
2) Pleural effusions
Infected effusion (complicated parapneumonics, empyema)
Malignant or benign effusions requiring bedside pleurodesis
Hemothorax
Chylothorax
3) Postoperation
Thoracic, cardiac, or esophageal surgery
Thoracoscopy

The common complications encountered with chest tube insertion are malposition and obstruction, either by occlusion or by kinking; ectopic insertion and tension pneumothorax with significant air leak; hence the need to secure the tube properly (17).Large and medium bore chest drain incisions are usually closed by a suture appropriate for a linear incision(7). Various techniques have been described, but a simple technique of anchoring the tube has not been the subject of a controlled trial (9). A purse string or U-suture placement (horizontal mattress suture) is used to aid removal of the chest drain at a

later date and facilitate closure of the defect on removal of the drain while avoiding the occurrence of an iatrogenic pneumothorax (3,16).

For this technique, the chosen suture should be stout, strong and non-absorbable (silk or prolene) to prevent ease of breakage (7). One or two additional simple or horizontal mattress sutures of generous depth should be placed to properly anchor the tube (7). This suture is also thought to prevent air reentry on drain removal as well as aid in chest drain site healing by apposing the edges of the wound (16). The suture is often tied to close the skin wound snugly around the tube to prevent any peri-tubal leak (4). However, this can result in an unsightly scar and tying this suture and retaining the knot for the purpose of achieving air and water tightness of the incision can worsen the painful experience of patients before and after drain removal. In addition, any delay in tube removal often increases the risk that is inherently associated with the retained suture being a foreign body (16). In other to increase the cosmetic appearance of the scar as well as provide an airtight seal to prevent air re-entry, attempts have been made to place an absorbable suture at the time of drain insertion but such methods may be cumbersome and complicated (16). Some centers have reported significant success with achieving airtightness using single barbed absorbable suture material(15).

Some commercially available dressings which adhere tightly to the skin and then attach to the drain may also be used but they do not replace the need to stitch the drain firmly in place (10). Another common method is to cover the wound with a water impermeant occlusive dressing material like vaseline gauze or adhesive tape, after removing the chest tubes to prevent air entry into the pleura but the cosmetic result may be unreliable with the wound healing by granulation (11).Petroleum-coated gauze as an occlusive seal was used in the past but it is no longer recommended because it leads to integument breakdown, wound infections, pneumothorax and wound dehiscence (2,7).

Other newer techniques for the management of the chest drain wound after tube removal such as a 2layer method with triclosan-coated sutures have been described(2). This method was designed with lots of advantages such as non-requirement of a stitch removal at follow-up, good wound healing with cosmetically-appealing scars; without an increased risk of infection but it has a drawback of being too expensive with requirement of technical expertise limiting its widespread adoption (2,3).

Sutures may not be necessary, after all, for closure of chest drain site as a study reported very minimal complications when sutures were not used(16). The study showed that the rate of acute pneumothorax after removal was 1.2% as opposed to the documented rate of 6%-10.7% for purse-string sutures. Late pneumothorax rate was 0% and only superficial infections occurred with this method which did not result in empyema thoracis as opposed to the documented rate of 1%-25% for purse-string suture use (16,21,22). There was also a reduction of the cost per patient which was not just from avoiding using a suture but also avoiding the cost of removing such a suture afterwards (16).

The optimal timing and criteria for tube removal is still a matter of controversy for many reasons (9). Some guidelines state that the criteria for chest drain removal should include no air leak and a 24- hour period of drainage of less than 500 mL fluid(16). Others state that the lung should be fully expanded and there should be no persisting hemothorax or pneumothorax, no air leak, no fresh or altered blood should be leaking from the site of insertion and the daily drainage should be <100 ml(10). Apparently, the timing of removal is dependent on the original reason for insertion and clinical progress and the common grand norm is tube removed when therapeutic goals have been achieved (7,9,16). Some studies recommend that the International Normalized Ratio (INR) should be regarded as a relative contraindication with decision left to the discretion of the individual managing physician.

When a purse-string suture is intended to be used for wound closure at the time of tube removal, the set up should involve two persons with one tying the knot of the purse-string to appose the wound edges immediately after the other person briskly removes the tube with a firm pull on it, after detaching the tube anchor stitches while the patient performs a Valsalva maneuver or during expiration (7). The actions of the two persons and the patient should be done in a coordinated and synchronous manner to avoid iatrogenic suck-in pneumothorax during the tube removal process. When a simple adhesive Tegaderm b Pad (3M, Saint Paul, MN) dressing was used for occluding the thoracostomy wound at time of tube removal in a study, the chest tube was removed under arrested expiration (the Valsalva maneuver) (16). Studies have demonstrated that the removal of thoracostomy tubes at the end of inspiration or at the end of expiration is equally safe (23). The rule should be that a chest tube should not be pulled out when the patient is still breathing actively because this will result in a pneumothorax (10).

In the study employing occlusive dressing for thoracostomy wound management after tube removal, clinical and wound complication rates (early and late) were significantly lower in comparison to previously published reports on purse-string suture use (16). Though with limitation of being a report from a single surgeon and single institution practice, it was still able to offer a safer alternative to the commonplace practice of purse-string closure technique. Table 2 below summarizes the complications and their rates amongst 312 patients requiring chest tube insertion over an 18-month period in whom only occlusive dressings with Tegaderm þ Pad (3M, Saint Paul, MN) was applied to the thoracostomy wound at the time of chest tube removal.

Complication	n (%)
Superficial wound infection	5 (1.6)
Acute pneumothoraces	4 (1.3)
Serous discharge requiring suture	1 (0.3)

	Table 2: Com	plication and rat	es after occlusiv	ve dressings at	time of chest	tube removal (16)
--	--------------	-------------------	-------------------	-----------------	---------------	-------------------

Though these findings may suggest superiority of this approach to thoracostomy wound management at time of chest tube removal, its reproducibility and generalizability should be done with caution since all the chest tubes were inserted as an adjunct to thoracic surgical procedures.

